2.2.7 Correlative Science Background

2.2.7.1 Correlative Laboratory Studies

Preclinical and clinical work in the Steele Lab and elsewhere has identified the stromal-derived factor 1 alpha (SDF1 α) as an attractive candidate for biomarkers of resistance to various therapies, but its role after proton beam radiation therapy is unknown. Based on findings from preliminary studies, we propose here to evaluate the changes in blood circulating SDF1 α and circulating myeloid cells to explore potential associations between the changes in these biomarkers and resistance to treatment. These biomarkers will be monitored from baseline throughout FOLFIRINOX therapy, before and after a one-week schedule of proton beam radiation therapy (or a two-week schedule of photon radiation), after pancreaticoduodenectomy, and at time of disease progression. In exploratory studies, we will evaluate several other cytokines using multiplex protein array (Meso-Scale Discovery, Inc.).

Circulating cell populations will be evaluated by fluorescence-based flow cytometry. Protein concentration in plasma will be measured using ELISA kits for SDF1 α and MSD multiplex kits for cytokines (IL-1, IL-6, IL-8 and TNF- α) vascular growth factors (VEGF, sVEGFR1, PlGF

and bFGF). These techniques have been used in the Steele Lab for over 8 years to evaluate patients' samples.

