5.5 Duration of Follow Up

Study participants will be in active follow up after completion of neoadjuvant treatment and surgery per study guidelines, as outlined above, except in the case of documented progression, at which time they will be followed for survival only. Participants removed from study for

unacceptable adverse events will be followed until resolution or stabilization of the adverse event.

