5.6 Criteria for Removal from Study

Participants will be removed from study when any of the criteria listed in Section 5.4 applies. The reason for study removal and the date the participant was removed must be documented in the study-specific case report form (CRF). Alternative care options will be discussed with the participant.

In the event of unusual or life-threatening complications, participating investigators must immediately notify the Principal Investigator [name]. at [REDACTED]

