8.1 Experimental Design

Blood will be drawn by venipuncture, and the first 7-10 ml blood will be excluded or used for other analysis. The following 8 ml will be collected in an EDTA tube. The EDTA tube with the blood sample will be shipped in wet ice within 2 hours of drawing for further processing at Steele Laboratory at MGH. We will analyze the correlation between plasma SDF1 α and circulating myeloid cells with multiple measures of outcome (ORR, TTP, OS) in patients with borderline resectable pancreatic cancer before, during, and after treatment.

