8.2 Collection

To this end we will measure circulating biomarkers at the following stages:

- (i) Pretreatment
- (ii) At beginning and end of FOLFIRINOX therapy
- (iii) After radiation therapy
- (iv) One month post-operatively
- (v) At the time of disease progression

Samples will be collected at the following timepoints:

- a. Prior to the start of therapy
- b. Day 8 of Cycle 1 of FOLFIRINOX
- c. After Cycle 4 (and Cycle 8 if received) of FOLFIRINOX
- d. After chemoradiation OR pre-operatively
- e. 1 month after completion of therapy.
- f. 1 month after pancreaticoduodenectomy (Whipple procedure)

g. Within 2 weeks after radiologic progression

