- (4) Nutritional assessment will include meeting with an oncology nutritionist for evaluation and education at the beginning of treatment. The patient will then track dietary protein intake throughout treatment until time of surgery. The patient's logged protein intake will be reviewed in post-op follow up by the treatment team. Both the nutritionist evaluation and protein tracking are optional resources available to patients and are not required by the protocol.
- (5) Peripheral blood for correlative studies will be obtained with clinical labs at pretreatment, day 8 of Cycle 1 FOLFIRINOX, at restaging visits, after proton beam radiation therapy/pre-operatively, 1 month after completion of therapy, 1 month post-operatively, and within two weeks of radiographic progression (these blood draws are optional).

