Mutational analysis: The frequency of genetic mutations characterized by the SNaPshot platform (sections 2.6.1 and 8.1) will be summarized. A sample size of 50 patients will provide 90% confidence intervals of maximal width $\pm 12\%$, but the interval widths will be narrower in practice as the mutation rates are typically quite low. We shall analyze PFS differences by mutational status if 5 failure events have been observed within each mutational subgroup. However, the analysis will be purely exploratory due to the limited numbers expected per mutation subgroup.

Circulating biomarkers: The association between plasma SDF1 α and circulating myeloid cells with outcome measures will be examined by logistic regression for ORR or by Cox regression for TTP and OS. Pretreatment levels as well as the changes during and after treatment from baseline will be analyzed. Biomarker levels are typically log-transformed

for analysis, but we shall also consider other approaches such as categorizing based on the observed distribution or dichotomizing at the median.

Patient-reported outcomes: We will use descriptive statistics to describe QOL (EORTC QLQ-C30), symptom burden (ESAS-r) and mood (HADS) for the entire study cohort. Mean values and standard deviations will be used to describe QOL and symptom burden (T-test or Wilcoxon as appropriate). We will score the HADS subscales for depressive and anxiety symptoms categorically, using a cut-off of >7 to describe the proportion of patients with these symptoms. We will use Chi-square or Fisher's Exact Test, as appropriate, to analyze the categorical variables.

Health care utilization: We will use descriptive statistics to describe hospitalizations, ICU stays, ED visits and palliative care use for the entire study cohort. Mean values and standard deviations will be used to describe continuous variables (T-test and Wilcoxon rank sum, as appropriate). We will use Chi-square or Fisher's Exact Test, as appropriate, to analyze the categorical variables.

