14.5 Reporting and Exclusions

All patients who begin protocol treatment will be included in the analysis of all the primary and secondary endpoints, except for the surgical outcomes as noted in 14.4.

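### Must Section 14.4 name the blood draw paired with each outcome in the circulating-biomarker models?

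*Combined protocol and SAP*

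**What the plan says.** Section 14.4 (Circulating biomarkers) names logistic regression for ORR and Cox regression for TTP and OS. On the covariate it says only "Pretreatment levels as well as the changes during and after treatment from baseline will be analyzed". Section 8.1 (Experimental Design) gives the same outcomes: "multiple measures of outcome (ORR, TTP, OS) in patients with borderline resectable pancreatic cancer before, during, and after treatment".

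The draws are listed in three places.
- Section 2.2.7.1 runs the series from baseline to "after pancreaticoduodenectomy, and at time of disease progression".
- Section 8.2 (Collection) presents its stages as serving the outcome correlation. It ends with a sample taken "Within 2 weeks after radiologic progression".
- Section 9, note (5), lists "pretreatment, day 8 of Cycle 1 FOLFIRINOX, at restaging visits, after proton beam radiation therapy/pre-operatively", then later draws including one at progression, and makes all of them optional.

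Three other rules bear on who has a sample.
- Section 5.5 keeps patients in active follow-up "except in the case of documented progression, at which time they will be followed for survival only".
- Section 5.6 says "Participants will be removed from study when any of the criteria listed in Section 5.4 applies", and progression is one of those criteria.
- Section 14.5 says "All patients who begin protocol treatment will be included in the analysis of all the primary and secondary endpoints", and excepts only surgical outcomes.

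Sections 10.1.3 to 10.1.5 define PFS, time to death and time to local recurrence. They do not define TTP.

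**The concern.** The progression sample exists because the TTP event has happened, and the date of a patient's last sample depends on how long that patient stayed event-free. If either is a fixed covariate measured from enrolment, the sampling time carries outcome information. A marker that drifts over time, or shifts at progression, then correlates with TTP and OS without having prognostic value.

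Three features of the text make this more than fanciful. Section 8.2 lists the progression draw among the stages that serve the outcome correlation. The scientific question is resistance, which makes that sample attractive. And early progressors have no later scheduled draw, while Section 14.5 read literally keeps every treated patient in every analysis, which could push an analyst towards the last available value.

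Two lesser points go with it. Draws after chemoradiation or surgery come after response to induction has been judged, so they cannot predict ORR. And without a TTP definition, the handling of deaths without progression is open. At stake is a marker reported as one of resistance when it is only a product of sampling time.

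**Working it through.** **Inputs.** The documents give n = 50 and accrual over 4 years (Section 14.2), and the draw list (Sections 8.2 and 9). They give no figure for this analysis to reproduce, no test level and no marker behaviour. The following are assumptions:
- TTP exponential with median 8, 12 or 18 months; OS = TTP plus an exponential time with median 8 months
- uniform accrual over 48 months, data cutoff at month 60
- scheduled draws at 0.25, 2, 4, 5 and 7 months, taken only while event-free
- nominal two-sided 5% as a yardstick

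**Model.** Change from baseline = drift × min(draw time, cap) + N(0,1), in SD units, with no true effect on risk. As an alternative, there is no drift but a step at progression. Each setting had 3,000 trials, so the simulation standard error at 5% is √(0.05 × 0.95 / 3000) = 0.4 percentage points.

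**False-positive rates** (ranges over the three medians):

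| Covariate | Marker behaviour | TTP | OS |
|---|---|---|---|
| Any | no drift, no step | 4-6% | 4-6% |
| Progression sample | 0.05 SD/month to month 6 | 6-7% | 6-7% |
| Progression sample | 0.05 SD/month to month 12 | 14-22% | 10-12% |
| Progression sample | 0.05 SD/month, no cap | 74-86% | 33-55% |
| Progression sample | 0.2 SD/month to month 6 | 19-39% | 12-16% |
| Last available sample | 0.05 SD/month to month 6 | 6-8% | 6-7% |
| Last available sample | 0.2 SD/month to month 6 | 18-38% | 15-19% |
| Last available sample | step of 1 SD at progression | 19-65% | 9-35% |
| One scheduled draw (month 5), event-free patients | every setting | 4-6% | 4-6% |

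The last row is the same whether time runs from enrolment or from the draw. It also survives irregular timing: with the draw anywhere in months 4-7 or 3-8 and drift of 0.05 or 0.2 SD/month, rates stay at about 5-6%.

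A second set of assumptions (median TTP 10 or 15 months, SD of change 0.5 log units, 1,000 trials per setting) agrees in pattern. The day 8 change gives 4.3-4.4% and the month-5 draw in event-free patients 5.9-6.2%. With a trend of ±0.1 log/month, the last sample including the progression draw gives 37-53% for TTP.

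**Does Section 14.5 force the bad version?** Expected number event-free at time t = 50 × 0.5^(t/median).
- At day 8 (0.25 months): 50 × 0.5^(0.25/8) = 48.9; median 12 gives 49.3; median 18 gives 49.5. A day 8 change can therefore cover almost everyone, early progressors included, subject to uptake of the optional draws.
- At month 5: 32.4, 37.5 and 41.2. Later draws lose patients, which an analyst would report as the number analysed.

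Section 14.5 cannot be literal here in any case. The draws are optional, so a full 50 is not assured even at baseline, and Section 10.2.2 already limits response to evaluable participants.

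**ORR.** Section 14.4 and the opening of Section 8 promise association, not prediction. A rule confining ORR models to draws up to restaging would not even secure prediction. Section 9 places the scans after the first week of cycle 4 and in the first week of the last cycle, while Section 8.2 takes samples after cycle 4 and after cycle 8, so those samples coincide with or follow the scan.

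**The case for a change.** The best case for a change is that the progression draw is collected for the stated purpose of correlating markers with outcome, that nothing excludes it from the TTP and OS models, and that a few words would close the gap at no cost. Section 14.4 also leaves the functional form open (log, categories or median split), so an unfixed draw adds to the analyst's freedom. Under strong or long-lasting drift, or a clear shift at progression, the distortion is large.

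Most of this is true as description. The omission is real, TTP is undefined, and the mechanism is sound. What does not follow is that the plan contains a faulty analysis. No sentence makes the progression sample or the last available sample a covariate; listing a collection time is not a plan to regress TTP on it. The removal and follow-up rules in Sections 5.4 to 5.6 mean that most scheduled draws already come from event-free patients, so the ordinary reading gives the sound analysis. The large percentages need drift or a step that the documents neither state nor imply; at 0.05 SD/month to month 6, even the poor choices give only 6-8%.

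**Conclusion.** No change is needed. The plan omits detail on an optional, exploratory analysis. Circulating biomarkers appear in no numbered objective of Section 1.3, and the R0 rule of at least 16 of 50 does not depend on them. A trial statistician would take scheduled draws one at a time in patients event-free at each, describe the progression sample or relate it to survival counted from that sample (5-6% false positives in every setting), and use the PFS definition of Section 10.1.3 or state how deaths count towards TTP. Done that way, error stays near 5% in every setting tried.

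The conclusion would weaken if a report used progression or last-available samples as fixed covariates from enrolment; a reader of the results should check for that. Every rate quoted rests on assumed medians, drifts, caps, steps and draw months. They show that the choice of draw can matter; they do not measure a defect in this plan.

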1.3 Secondary Objectives

- 1.3.1** To determine the progression-free survival of patients who receive preoperative FOLFIRINOX and preoperative short-course radiation therapy.
- 1.3.2** To determine overall survival in patients treated with preoperative FOLFIRINOX and short-course radiation therapy.
- 1.3.3** To determine the toxicity of FOLFIRINOX + short-course radiation therapy in patients with pancreatic cancer.
- 1.3.4** To determine the surgical morbidity in patients undergoing pancreaticoduodenectomy or distal pancreatectomy who received preoperative FOLFIRINOX and preoperative short-course radiation therapy.
- 1.3.5** To determine 30-day post-operative mortality after pancreaticoduodenectomy or distal pancreatectomy in patients who receive preoperative FOLFIRINOX and short-course radiation therapy.
- 1.3.6** To determine pathologic downstaging of FOLFIRINOX + short course radiation therapy.

- 1.3.7** To determine local control rates with FOLFIRINOX + preoperative short-course radiation therapy.
- 1.3.8** To correlate mutational analysis biomarkers (SNaPSHOT assay) with response to treatment.
- 1.3.9** To describe quality of life, symptom burden and mood in the study population
- 1.3.10** To measure utilization of health services (emergency room, hospital and intensive care unit) in the study population

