A randomized trial comparing the efficacy of gemcitabine and FOLFIRINOX in metastatic pancreatic cancer also assessed QOL, using the European Organization for the Research and Treatment of Cancer QOL Questionnaire C30 (EORTC QLQ-C30).[7] The authors demonstrated that FOLFIRINOX not only prolonged survival, but also significantly reduced QOL impairment compared to gemcitabine for patients with metastatic cancer. Thus, in addition to the utility of describing the symptom burden and QOL in patients with borderline resectable pancreatic cancer, it will also be useful to compare these outcomes in patients receiving different chemotherapy regimens.

We will use the EORTC QLQ-C30, a validated instrument designed for prospective clinical trials that evaluates five functions (physical, role, cognitive, emotional, and social), and nine symptoms (fatigue, pain, nausea and vomiting, dyspnea, loss of appetite, insomnia, constipation, diarrhea, and financial difficulties) to measure QOL.[15] We will use the Edmonton Symptom Assessment System-revised (ESAS-r) to measure symptoms, which has been previously validated in patients with advanced cancer.[16] The ESAS-r consists of ten items assessing pain, fatigue, drowsiness, nausea, anorexia, dyspnea, depression, anxiety, well-being, and a free-response item. We will include constipation as the free-response item. The ten items are scored

on a scale of 0-10 (0 reflecting no reported presence of the symptom and 10 reflecting the worst possible severity of the symptom). We will instruct patients that items are to be rated based on the previous 24-hour period. We will use the Hospital Anxiety and Depression Scale (HADS) to assess symptoms of depression and anxiety.[17] The HADS is a 14-item questionnaire that contains two 7-item subscales assessing depression and anxiety symptoms during the past week. The questionnaire consists of a four-point item response format that quantifies the degree to which participants experience a particular emotion. Scores on each subscale range from 0 to 21, with a cutoff of 8 or greater denoting clinically significant depression or anxiety symptoms.

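### The HADS 0-21 scores are analysed only as 8 or more versus 7 or less; keep that proportion, but add means and within-patient change

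*Combined protocol and SAP*

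**What the plan says.** - **Objective 1.3.9** is descriptive: "To describe quality of life, symptom burden and mood in the study population".
- **HADS in 14.4:** "We will score the HADS subscales for depressive and anxiety symptoms categorically, using a cut-off of >7". The stated purpose is to give the proportion of patients with these symptoms. For categorical variables: "We will use Chi-square or Fisher's Exact Test, as appropriate, to analyze the categorical variables". The plan does not say which groups or time points are compared.
- **The other two instruments in 14.4:** "Mean values and standard deviations will be used to describe QOL and symptom burden (T-test or Wilcoxon as appropriate". Pairing is not mentioned here either.
- **Basis for the cut** (PRO background, 2.2.7.1): "Scores on each subscale range from 0 to 21, with a cutoff of 8 or greater denoting clinically significant depression or anxiety symptoms". On an integer score, >7 and 8 or more are the same split, so the two sections agree.
- **Schedule** (8.2 Patient Reported Outcomes): all three questionnaires are completed at consent, at weeks 3, 7, 11 and 15 of FOLFIRINOX, in week 2 of chemoradiation, and in follow-up.

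No HADS mean, SD or change score is planned anywhere in the document.

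**The concern.** HADS is the only patient-reported instrument reduced to yes/no, and it is the one named for mood. After the cut, scores of 8 and 20 count alike, as do 0 and 7. A patient who moves from 8 to 16, or from 1 to 7, registers no change. Even a purely descriptive report would then lack the location, spread and severity of the scores. With at most 50 patients, and probably fewer at later visits, a change in mood visible in the scores may not be visible in the proportion.

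A second, smaller point concerns the tests. Chi-square and Fisher's exact test assume independent samples. If they were used to compare time points in the same patients, they would ignore the pairing.

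**Working it through.** **1. The plan's own figure.** The documents state no power, effect size or precision for HADS. The 50 patients come from the R0 rule in 14.2 (at least 16 of 50). Exact binomial: P(X ≥ 16 | 50, 0.20) = 0.031 and P(X ≥ 16 | 50, 0.40) = 0.904, which reproduces the stated 3% and 90%. The sample size therefore says nothing about mood.

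**2. Information kept by the cut.** For a normal score split so that a fraction p lies above the cut c, the efficiency relative to the full score is φ(c)²/[p(1−p)].

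| p above cut | φ(c) | Efficiency |
|---|---|---|
| 10% | 0.1755 | 0.1755²/0.09 = 0.34 |
| 20% | 0.2800 | 0.2800²/0.16 = 0.49 |
| 30% | 0.3477 | 0.3477²/0.21 = 0.58 |
| 50% | 0.3989 | 0.3989²/0.25 = 0.64 |

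The split loses about 36-66% of the information over this range.

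**3. Power for a within-patient shift.** Every HADS input is an assumption. Two correlated normal scores are rounded and truncated to 0-21 and tested at two-sided 0.05. With mean 5 and SD 3.5, the fraction above 7 is 1 − Φ((7.5 − 5)/3.5) = 0.24. After a 1.5-point shift it is 1 − Φ((7.5 − 6.5)/3.5) = 0.39.

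Results with correlation 0.5 and 2,000 replicates (Monte Carlo SE up to 1.1 points), power in %:

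| Pairs | Mean/SD | Shift | Paired t | McNemar, exact | Unpaired t | Chi-square | Fisher |
|---|---|---|---|---|---|---|---|
| 50 | 5/3.5 | 1.5 | 81 | 38 | 57 | 33 | 25 |
| 50 | 6/4 | 1.5 | 72 | 33 | 44 | 29 | 21 |
| 50 | 5/3.5 | 2 | 97 | 66 | 88 | 60 | 52 |
| 50 | 6/4 | 2 | 93 | 56 | 74 | 53 | 44 |
| 35 | 5/3.5 | 2 | 89 | 46 | 69 | 44 | 34 |
| 35 | 6/4 | 2 | 81 | 40 | 56 | 34 | 23 |

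The comparison must be like for like. Paired t against McNemar isolates the cut, and so does unpaired t against chi-square. Setting paired t against chi-square would mix the cut with the loss of pairing.

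**4. Range.** With 50 pairs, baseline mean 5-7, SD 3.5-4 and correlation 0.4-0.6:

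- 1.5-point shift: about 66-90% (paired t) against 30-44% (McNemar); unpaired, 43-60% (t) against 29-35% (chi-square).
- 2-point shift: about 89-99% (paired t) against 54-73% (McNemar).

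A repeat with 4,000 replicates and fresh random numbers gave 66-90% against 33-43%, and 87-99% against 52-71%. The two runs agree to within about 3 points.

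**The case against.** **The cut answers a stated question.** The PRO background says that the prevalence of depression by disease stage is poorly studied, and gives 8 or more as clinically significant. This stands. The split is prespecified and clinically based, and the proportion should stay as the prevalence summary.

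**No test of change is planned.** The aim is to describe, and 14.4 specifies no change-from-baseline comparison for any patient-reported outcome. The one comparison the background mentions is between patients on different chemotherapy regimens, for which independent-sample tests would fit. This also stands. The power figures show how much information the cut gives up; they do not show that a planned test fails. The named tests are under-specified, as they are for QOL and symptoms, and cannot be called wrong as written.

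**Mood is measured elsewhere.** "The ESAS-r consists of ten items assessing pain, fatigue, drowsiness, nausea, anorexia, dyspnea, depression, anxiety, well-being, and a free-response item". The QLQ-C30 has an emotional function scale. Both are summarised by means at the same visits. They are a partial backstop: the ESAS-r gives depression and anxiety one item each, against seven per HADS subscale.

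**A stronger reading.** A reader might infer that a change in mood would mostly be missed, or that the trial could report none while its own forms show one. The documents do not support this. With all 50 patients and a 2-point shift, McNemar on the split detects more than half under these assumptions, and chi-square 53-60% in the table. At 3 points (mean 5, SD 3.5) chi-square reaches about 95%. The other two instruments would also give continuous readings.

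**Conclusion.** The point holds as a minor, nearly free improvement. HADS is the only instrument cut to yes/no, and no score-level summary is planned although the scores are collected. Compared like for like with 50 pairs, the paired score analysis has roughly twice McNemar's power for a 1.5-point shift, and a smaller but clear advantage at 2 points. With 35 pairs and a 2-point shift, the table gives 81-89% against 40-46%.

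These sizes depend on an assumed baseline mean, SD, correlation, shift and alpha, none of which the documents give. The qualitative point does not: a proportion above 7 cannot describe severity or any movement on one side of the cut. Nothing here affects the R0 endpoint, the sample size or safety.

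**What to change.** In the patient-reported outcomes paragraph of 14.4:

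1. Keep the proportion above 7 on each HADS subscale as the prespecified prevalence summary.
2. Add, for HADS-D and HADS-A, the mean and SD at each time point, and the within-patient change from baseline with a 90% CI (the level used elsewhere in 14.4), by paired t-test or Wilcoxon signed-rank test.
3. State that if the proportion above 7 is compared between time points in the same patients, McNemar's test replaces Chi-square or Fisher's exact test.

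The cost is two or three sentences and a few more rows in one table. There is no new questionnaire, visit or data item.
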